STUDY PROTOCOL

EFFICACY OF PC6 ELECTROACUPUNCTURE IN THE PREVENTION OF NAUSEA VOMITING IN CAESAREAN PATIENT UNDER SPINAL ANAESTHESIA

NMRR ID: 19-3279-51524(IIR)

Date: 4th MARCH 2020

Sponsor: Self-sponsored study

Institution:

Hospital Raja Permaisuri Bainun Ipoh

Sampling Method

Potential study subject is identified when booking for elective is made to the Maternal Operating Theatre. Upon identification of potential subject, the patient shall be seen by the anaesthetic doctor in the ward for recruitment purposes a day before the operation (patient scheduled for elective LSCS will be admitted a day before in maternal ward and will be seen by anaesthetist in the ward a day before). The patient is then further assessed by investigators for suitability for recruitment into the study, and if the patient fulfils the criterion, patient is then counselled for enrolment into the study. Patient will be informed on the study objectives, electroacupuncture and its potential side effects including minimal discomfort over the puncture site, redness after removal of needle. They will also be informed that randomization will take place and that they may receive granisetron and sham acupuncture or electroacupuncture and granisetron.

Subsequently, assessment for data collection will also be explained to them i.e. nausea and vomiting assessment. The subject will be informed regarding circumstances where they will be excluded or withdrawn from the study. Upon agreement for enrolment, informed consent form will be provided to the patient and explained in detail the process of randomisation, study procedure including procedures for provision of spinal anesthesia, method of assessment postoperatively, as well as the potential side effects of electroacupuncture before they sign and date on the informed consent form. Once the patient agreed to get enrolled, she will be consented a day before the operation.

When the patient is successfully enrolled, by using simple randomization they will be assigned to one of two groups (EA or sham group) using sealed envelope method. Sham group

shall receive 1mg of IV granisetron and sham acupuncture while the EA group shall receive 1mg of IV granisetron and electroacupuncture throughout the surgery.

The identity of the envelop shall only be known by an independent assisting nurse and acupuncture performer (In this study, principal investigator will be the acupuncture performer).

Study protocol

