Adverse effect and management- As the puncture site is safe (over the hand, away from main vessels) and the needle is tiny, it can rarely cause serious adverse event. The most serious event will be syncopal which happens in needle phobia patient (who will be not be included in the study during recruitment) and interference with pacemaker (exclusion criteria in this study), the most common drawback of the

acupuncture practice couple using electroacupuncture machine will be pain and hematoma at the needle insertion site but is usually transient and self-limiting. Furthermore it is done in a controlled environment (operation theatre) with resuscitation equipment and experience personnel further ensure the safety of subjects. In the cases of study related injury, patient will receive necessary treatment in Hospital Raja Permaisuri Bainun until recover.

Sample Size

Objective 1:

For this study, it is expected the incidence of IONV in granisteron group to be 52%, whereas for electroacupuncture and granisetron group, 22%.

Power and Sample size Program, ScalexProp version 1.0.2 (Naing, 2016) is used to estimate the sample size for this objective. It is planned that this study consists of independent cases and controls with 1 control(s) per case. Prior data indicate that the failure rate among controls is 0.52. If the true failure rate for experimental subject is 0.22, 37 experimental (electroacupuncture+granisetron) subjects and 37 control (granisetron alone) subjects will be needed to be able to reject the null hypothesis that the failure rates for experimental and control subjects are equal with probability (power) 0.8. The Type I error probability associated with this test of this null hypothesis is 0.05.

Including 20% potential drop out rate, the sample size needed for this study is 88 patients (44 for electroacupuncture+granisetron arm and 44 for granisetron arm).

Objective 2:

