No prior research was done using a recommended dose 1mg of granisetron in cesarean section patient for reduction in incidence of PONV up to 24 hours. However there is a RCT done in 2017 by Chang Yen Yin et al comparing the efficacy of acupuncture plus ondansetron versus ondansetron after bupivacaine-morphine spinal anesthesia, this study showed that the incidence of PONV up to 24 hours were 43% in ondansetron group versus 16% in acupuncture plus ondansetron. Since most of the literature stated the 5HT3 antagonist drugs (4mg IV ondansetron and 1mg IV granisetron) have similar efficacy to prevent PONV.

For this study, it is expected that the incidence of PONV in granisetron group to be 43%, whereas for electroacupuncture and granisetron group, 16%.

Power and Sample size Program, ScalexProp version 1.0.2 (Naing, 2016) is used to estimate the sample size for this objective. We are planning a study of independent cases and controls with 1 control(s) per case. Prior data indicate that the failure rate among controls is 0.43. If the true failure rate for experimental subject is 0.16, we will need to study 41 experimental (electroacupuncture+granisetron) subjects and 41 control (granisetron alone) subjects to be able to reject the null hypothesis that the failure rates for experimental and control subjects are equal with probability (power) 0.8. The Type I error probability associated with this test of this null hypothesis is 0.05.

Including 20% potential drop out rate, the sample size needed for this study is 98 patients (49 for electroacupuncture+granisetron arm and 49 for granisetron arm).

Data Collection

Postoperative data collection shall be done by trained APS team. The details to be filled in the form include patient general demographic data (Age, gender, weight), anaesthetic regime (dosage of heavy bupivacaine 0.5%), indication of caesarean section (breech presentation, one previous scar refuse vaginal birth), intraoperative exteriorization of uterus, as well as duration of surgery in minutes.

Nausea and vomiting are then assessed intraoperatively in operating theatres and post operatively in recovery room and ward. Retrospective assessment will be done by study team in ward to assess nausea and vomiting incidence at 0-12 Hrs post operation and 12-24 hrs post operation.

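### IONV (Objective 1) and PONV to 24 h (Objective 2) are each sized at the full 0.05, with no primary outcome or testing order in the available text; if a win on either is claimed, the two-sided family-wise error can reach 9.75%

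*Protocol*

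**What the plan says.** The protocol's title sets one question: "EFFICACY OF PC6 ELECTROACUPUNCTURE IN THE PREVENTION OF NAUSEA VOMITING IN CAESAREAN PATIENT UNDER SPINAL ANAESTHESIA".

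The Sample Size section then splits it into two objectives, each with its own calculation.

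- **Objective 1 (IONV):** "it is expected the incidence of IONV in granisteron group to be 52%, whereas for electroacupuncture and granisetron group, 22" per cent. The result is that "37 experimental (electroacupuncture+granisetron) subjects and 37 control (granisetron alone) subjects will be needed". With 20% dropout the total is 88.
- **Objective 2 (PONV to 24 h):** "it is expected that the incidence of PONV in granisetron group to be 43%, whereas for electroacupuncture and granisetron group, 16" per cent. The result is 41 per arm. With 20% dropout the total is 98.

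Both calculations ask for enough patients "to be able to reject the null hypothesis that the failure rates for experimental and control subjects are equal with probability (power) 0.8", and both state: "The Type I error probability associated with this test of this null hypothesis is 0.05".

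The objectives are numbered but not ranked. The available text does not call either outcome primary, co-primary, secondary or exploratory. It gives no testing order and no rule on whether one or both results are needed for a conclusion. Each calculation presents its own total as the size of the study.

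**The concern.** The design has two efficacy tests at full alpha and one overall question. The two results can plausibly differ: stimulation stops and the needles come out at the end of surgery (Study protocol section), while PONV is counted over the following 24 hours. A trial that is significant on one outcome and not the other has no pre-stated conclusion. If the favourable outcome could then carry the efficacy claim, the error rate of that claim would exceed the rate attached to either test.

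The numbering does not settle the matter. Objective 2 requires the larger sample, which is not what one expects of a clearly subordinate endpoint. Details of multiplicity adjustment may properly sit in a statistical analysis plan. Which outcome decides the trial is protocol content, and here the protocol itself fixes two full-alpha tests and two competing totals.

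**Working it through.** **Inputs from the Sample Size section.** Objective 1: 0.52 v 0.22, 37 per arm. Objective 2: 0.43 v 0.16, 41 per arm. Both: alpha 0.05, power 0.80, 1:1 allocation. The sidedness of alpha is not stated. The correlation between the two test statistics is not given either, so it is an assumption and is shown as a range.

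**1. Reproducing the stated sizes.** Unpooled two-proportion formula, no continuity correction:

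n = (z₁₋α/₂ + z₀.₈₀)² × [p₁(1−p₁) + p₂(1−p₂)] / (p₁−p₂)²

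At two-sided 0.05, (1.960 + 0.842)² = 7.849.

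- Objective 1: 7.849 × 0.4212 / 0.0900 = 36.73, so 37.
- Objective 2: 7.849 × 0.3795 / 0.0729 = 40.86, so 41.

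Both match exactly. With alpha 0.025 each, the same formula gives 44.5 and 49.5, so 45 and 50. The variants tried do not match: pooled two-sided gives 40 and 44, and one-sided with continuity correction gives 38 and 42. Each objective was therefore sized at the full two-sided 0.05.

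**2. Family-wise error if a win on either outcome counts.** Both nulls true, bivariate normal test statistics with correlation ρ:

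- Either direction: 1 − P(|Z₁| < 1.96 and |Z₂| < 1.96)
- Benefit only: 1 − P(Z₁ < 1.96 and Z₂ < 1.96)

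| ρ | Either direction | Benefit only |
|---|---|---|
| 0 | 9.75% | 4.9% |
| 0.3 | 9.5% | 4.8% |
| 0.5 | 9.1% | 4.5% |
| 0.7 | 8.3% | 4.2% |
| 0.9 | 7.0% | 3.5% |

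For a single test the figures are 5% and 2.5%. At ρ = 0 the first entry is 1 − 0.95² = 0.0975. With no model for the dependence, the Bonferroni bound is 10%.

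**3. How often the two tests would disagree.** The larger stated size is 49 per arm; less 20% this leaves 49 × 0.8 = 39.2, about 39 evaluable. Power of each test at two-sided 0.05 is Φ(d/√(v/n) − 1.96), where d is the difference in rates and v the sum of p(1−p) over the arms.

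- IONV: 0.30/√(0.4212/39) = 2.887, power 82%.
- PONV: 0.27/√(0.3795/39) = 2.737, power 78%.

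Under the protocol's own effects, simulation from the bivariate normal gives both tests significant in 64%, 69% and 71% of trials at ρ = 0, 0.5 and 0.7. Exactly one is significant in about 32%, 23% and 18%.

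**4. Cost of the remedies (39 per arm, ρ = 0.5).**

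| Rule | IONV | PONV |
|---|---|---|
| Two separate 0.05 tests, as written | 82% | 78% |
| IONV first, PONV only if IONV significant | 82% | 69% |
| Holm | 79% | 75% |

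**The case against.** The strongest reply is that nothing quoted is false. The protocol attaches each 0.05 to its own test and its own null hypothesis, and for each test it is right. It promises no trial-wide 5%. Nor does it say that a win on either outcome is enough. If intraoperative and postoperative events are reported as two separate conclusions, whether to adjust is debatable. If both results were required, the error would not exceed 5%. All of this stands.

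A reader might infer that the trial simply has a 9% chance of a false efficacy claim instead of 5%. The documents do not support that. The figure needs a win-on-either rule that is not written, a correlation that is not given, and the counting of false results in both directions. An efficacy claim means benefit, and there the comparison is at most 4.9% against 2.5%. The relative inflation is the same or nearly so, but the absolute chance is about half.

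It can also be said that the statistical analysis plan is not at hand and that the available protocol text is partial: it uses the labels Objective 1 and Objective 2 without an objectives list. A designation may sit in text not shown, so the point is limited to what is available. It does not rest on a missing multiplicity procedure. It rests on two full-alpha calculations and two study totals that the Sample Size section states side by side without saying which governs.

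**Conclusion.** The point holds in a limited form. The available protocol text sets two efficacy tests, each at the full two-sided 0.05, names neither as decisive, and has no rule for a split result. Under its own assumed effects, a split would occur in about 18% to 32% of trials (39 evaluable per arm, correlation 0.7 to 0).

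If significance on either outcome were taken as showing prevention of nausea and vomiting, the two-sided family-wise error would be up to 9.75%, about 9.1% at correlation 0.5 and 7.0% at 0.9. This assumes bivariate normal statistics and no multiplicity rule elsewhere. The two-sided reading of alpha is inferred from the exact reproduction of 37 and 41. The trial remains interpretable, but its decision rule should be fixed before results are seen.

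**What to change.** Before unblinding, add to the Sample Size section one of the following.

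- **Fixed order.** Name one objective as primary, tested at two-sided 0.05. Test the other at two-sided 0.05 and claim it as confirmatory only if the first is significant; otherwise report it as exploratory. The order is the sponsor's choice. Objective 1 first follows the protocol's numbering.
- **Holm.** Use it across the two tests if both outcomes are to stand equally.

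Restate the Objective 2 power to match the chosen rule, and give one study total in place of both 88 and 98.

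The change takes a few sentences and needs no extra patients or data. The price is power for a confirmatory claim. With IONV first, PONV falls from about 78% to about 69% while IONV keeps about 82%. With PONV first, PONV keeps about 78% and IONV falls to the same 69%, the chance that both tests succeed. Holm gives about 79% for IONV and 75% for PONV. All of these assume about 39 evaluable per arm, correlation 0.5 and the protocol's effect sizes.

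### The 20% dropout allowance multiplies by 1.2 instead of dividing by 0.8, and two totals (88 and 98) are each given as the study's size, so the stated power is not secured

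*Protocol*

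**What the plan says.** The Sample Size section makes two calculations, one per objective, with the same error rates: "The Type I error probability associated with this test of this null hypothesis is 0.05", and the null hypothesis is to be rejected when the "failure rates for experimental and control subjects are equal with probability (power) 0.8".

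- **Objective 1 (intraoperative nausea and vomiting).** "Prior data indicate that the failure rate among controls is 0.52", and "If the true failure rate for experimental subject is 0.22, 37 experimental (electroacupuncture+granisetron) subjects and 37 control (granisetron alone) subjects" are required. After a 20% dropout allowance, "the sample size needed for this study is 88 patients (44 for electroacupuncture+granisetron arm and 44 for granisetron arm").
- **Objective 2 (postoperative nausea and vomiting to 24 hours).** "Prior data indicate that the failure rate among controls is 0.43", the experimental rate is taken as 0.16, and "we will need to study 41 experimental (electroacupuncture+granisetron) subjects and 41 control (granisetron alone) subjects". The closing statement is "Including 20% potential drop out rate, the sample size needed for this study is 98 patients", split as 49 per arm.

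The protocol text available has no sentence saying which total will be recruited, or that the larger one governs.

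**The concern.** A dropout rate is a fraction of those enrolled. If 20% of enrolled patients are lost, 80% remain, so the evaluable number must be divided by 0.8. Multiplying it by 1.2 adds 20% of the evaluable number, which is a smaller quantity. The totals of 88 and 98 look like the second operation, so neither would leave the number its own calculation requires.

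Separately, one trial has one enrolment figure, and this one has two, each described as what the study needs. A team that recruits to 88 would be working to a stated figure while being well short for Objective 2. What is at stake is the 80% power claim, and a clear recruitment target against which completion can be judged.

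**Working it through.** **Inputs (Sample Size, Objectives 1 and 2).** Alpha 0.05, power 0.80, 1:1 allocation, dropout 20%. Objective 1 rates 0.52 and 0.22; Objective 2 rates 0.43 and 0.16. Sidedness is not stated; two-sided is assumed because it reproduces the protocol's numbers.

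**Step 1: reproduce the evaluable numbers.** The unpooled two-proportion formula is n = (1.960 + 0.8416)² × [p1(1−p1) + p2(1−p2)] / (p1−p2)², with (1.960 + 0.8416)² = 7.849.

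- Objective 1: 7.849 × (0.2496 + 0.1716) / 0.30² = 7.849 × 0.4212 / 0.0900 = 36.73, so 37.
- Objective 2: 7.849 × (0.2451 + 0.1344) / 0.27² = 7.849 × 0.3795 / 0.0729 = 40.86, so 41.

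Both match the protocol.

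**Step 2: reproduce the inflated numbers.**

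| | Evaluable n per arm | n × 1.2 | Protocol per arm (total) | n / 0.8 | Per arm needed (total) |
|---|---|---|---|---|---|
| Objective 1 | 37 | 44.4 | 44 (88) | 46.25 | 47 (94) |
| Objective 2 | 41 | 49.2 | 49 (98) | 51.25 | 52 (104) |

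The protocol's figures are n × 1.2 with the fraction dropped. Each total is 6 patients below the one that matches a 20% loss. Rounding is not the main cause: 45 and 50 per arm would leave 36 and 40, still too few.

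**Step 3: what remains after a 20% loss.** 44 × 0.8 = 35.2, below 37. 49 × 0.8 = 39.2, below 41. The dropout actually covered is 1 − 37/44 = 15.9% and 1 − 41/49 = 16.3%.

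**Step 4: power with those numbers.** For the unpooled formula, power = Φ( (p1−p2) / √{[p1(1−p1) + p2(1−p2)]/n} − 1.960 ). For Objective 2 at n = 39: 0.27 / √(0.3795/39) = 2.737; 2.737 − 1.960 = 0.777; Φ(0.777) = 0.781. The pooled version, which corresponds to the usual chi-square test, uses the pooled variance in the critical value.

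| Enrolled, 20% loss | Evaluable per arm | Objective | Unpooled | Pooled |
|---|---|---|---|---|
| 98 | 39 | 2 | 78.1% | 75.3% |
| 98 | 39 | 1 | 82.3% | 79.5% |
| 88 | 35 | 2 | 73.7% | 70.6% |
| 88 | 35 | 1 | 78.1% | 74.9% |

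**Step 5: separate the two sources of shortfall.** With no dropout error at all, pooled power is already 77.3% (Objective 1, n = 37) and 77.5% (Objective 2, n = 41); unpooled it is 80.3% and 80.1%. So when each objective has its own stated total, the dropout error costs about 2 percentage points under either formula. The rest of the gap between 80% and the pooled values comes from the choice of formula, which is a different matter.

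**The case against.** The arithmetic is not in dispute; the objections concern its size and how it is presented.

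- **The effect is small if 98 is meant.** Each calculation sits under its own objective, and a reader would naturally take the larger total, which covers the smaller need. Objective 1 then has 39 evaluable per arm against 37 needed, and Objective 2 loses about two points of power. The rates are uncertain by more than that: the protocol says that no earlier study used this granisetron dose for 24-hour outcomes in caesarean patients, and it borrows the Objective 2 rates from an ondansetron trial. This stands, and it limits the weight of the point. It does not make the 20% statement true, because 98 still fails Objective 2 at that rate.
- **88 is nowhere called the recruitment target.** True, but neither is 98, and the wording attached to the two is the same. Some pages were removed from the copy reviewed, so the fair statement is that the text available does not choose.
- **The pooled figures mix in another issue.** This stands. The loss attributable to dropout is the roughly two points shown in Step 5, and any restated power should name its formula.
- **Equal arms are assumed.** Sampling Method specifies simple randomization with sealed envelopes, which does not guarantee 49 in each arm. This stands as a condition on the restated tolerance.

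**Conclusion.** The concern holds. The evaluable numbers are right for the formula used, but both dropout-inflated totals are too small for the 20% loss they claim to absorb, by 6 patients each, and the single enrolment target is not stated. At 98 enrolled and 20% loss, power is about 78% for Objective 2 and 82% for Objective 1. At 88 enrolled it is about 74% and 78%. The ambiguity between the totals can therefore cost Objective 2 more (about 6 points) than the inflation error alone (about 2 points).

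These figures rest on the protocol's own event rates, a two-sided 0.05 test, the unpooled formula, 20% loss in each arm and equal arms. This should be corrected, but it does not threaten the design.

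**What to change.** Name one enrolment figure covering both objectives, and make the dropout statement agree with it. There are two ways.

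1. **Keep 98 and restate what it delivers.** Suggested wording: *A total of 98 patients (49 per arm) will be enrolled for both objectives. With equal arms this retains 41 evaluable per arm for dropout up to about 16%. At 20% dropout (39 per arm), power by the unpooled two-proportion formula is about 78% for Objective 2 and 82% for Objective 1.* If a chi-square test is planned, give the pooled values as well (75.3% and 79.5%).
2. **Keep the 20% allowance and enrol 104 (52 per arm).** This leaves 52 × 0.8 = 41.6 per arm and also covers Objective 1.

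In either case, remove the claim that the study needs 88, or label it as the requirement for Objective 1 alone and correct it to 94.

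The first option costs only wording. The second adds 6 patients to the larger stated total.
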